7.1.1.1 Follow-up evaluation

Potential drug-induced liver injury events require follow-up monitoring as described in Table 10-2. Monitoring should continue until liver chemistry values normalize, stabilize, or return to Baseline. Determination of stabilization is at the discretion of the Investigator in consultation with the hepatologist (as applicable) and UCB Study Physician, as needed.

7.1.2 Clinical laboratory criteria

Study participants should be monitored for absolute neutrophil count $< 1.0 \times 10^3/\mu\text{L}$ and/or absolute lymphocyte count $< 0.2 \times 10^3/\mu\text{L}$.

Participants may remain in the study if the result is transient. A retest is required within 1 to 2 weeks at a scheduled or unscheduled visit. If the repeat absolute neutrophil count or absolute lymphocyte count is still below the allowable values, the participant must be withdrawn. If the repeat absolute neutrophil count or absolute lymphocyte count is above the allowable values, the participant may continue in the study.

7.1.3 Treatment interruptions/temporary discontinuation of study medication

Doses of IMP that were missed due to a reasonable interfering AE or exceptional circumstance, which does not allow administration of IMP due to safety reasons, will not result in the study participant being considered noncompliant. The AE or exceptional circumstance should be discussed immediately with the Medical Monitor.

Any considerations related to restarting IMP should be discussed with the Medical Monitor.

7.2 Participant discontinuation/withdrawal from the study

Participants are free to withdraw from the study at any time, without prejudice to their continued care.

A participant may withdraw from the study at any time at his/her own request, or may be withdrawn at any time at the discretion of the Investigator for safety, behavioral, compliance, or administrative reasons.

Investigators are expected to continually assess the balance of burden to each participant against the observed and anticipated clinical benefit, and to recommend study withdrawal if the benefit-risk balance is not favorable.

If the participant withdraws consent/assent for disclosure of future information, the Sponsor may retain and continue to use any data collected before such a withdrawal of consent/assent.

If a participant withdraws from the study, he/she may request destruction of any samples taken and not tested, and the Investigator must document this in the site study records.

See the Schedule of Activities ([Table 1-1](#) and [Table 1-2](#)) for data to be collected at the time of early discontinuation (Early Discontinuation Visit [EDV]) and follow up (SFU) and for any further evaluations that need to be completed.

Investigators should contact the Medical Monitor, whenever possible, to discuss the withdrawal of a participant in advance.

Participants must be withdrawn from the study if any of the following events occur:

1. Participants **must be referred** immediately to a mental healthcare practitioner (ie, licensed psychiatrist or clinical psychologist) for further assessment of any SIB and/or any evidence of major depression, if any of the following events occur:
 - Active suicidal ideation as indicated by a positive response (“Yes”) to Question 5 of the “Since Last Visit” version of the C-SSRS
 - Any suicidal behavior since last visit
 - Severe depression as indicated by a PHQ-9 score ≥ 20The mental health consultation will be documented in source documentation.
2. Participant or legal representative withdraws consent/assent to participate in the study.
3. There is confirmation of a pregnancy in a female study participant, as evidenced by a positive pregnancy test during the study. (For further information see [Section 8.3.5.](#))

4. The Sponsor or a regulatory agency requests withdrawal of the participant.
5. Participant has a diagnosis of active TB, an NTMB infection, or LTBI during the study. (For further information see Section 8.2.5.3.7.)
6. Participant has an IGA response ≥ 3 (on a scale from 0 to 4) at Week 20.

Investigators should contact the Medical Monitor to discuss whether a participant is to be withdrawn from the study if any of the following events occur:

7. Participant develops an illness that would interfere with his/her continued participation.
8. Participant or caregiver is noncompliant with the study procedures or medications in the opinion of the Investigator.
9. Participant takes prohibited concomitant medications as defined in this protocol (Section 6.5.2).
10. Participant does not tolerate the IMP.
11. Study participants **must be referred** immediately to a mental healthcare practitioner (ie, licensed psychiatrist or clinical psychologist) and may be withdrawn from the study based upon the Investigator's judgment of benefit/risk for either of the following:
 - Active suicidal ideation as indicated by a positive response (“Yes”) to Question 4 of the “Since Last Visit” version of the C-SSRS.
 - Moderately severe major depression as indicated by a PHQ-9 score of 15 to 19 if this represents an increase of 3 points compared to last visit.

The mental health consultation will be documented in source documentation.

12. Any study participant who develops a clinically important infection or recurrent infections not responsive to standard therapy during the study must:
 - Discontinue IMP until resolution of the infection.
 - The Investigator should use clinical judgement in deciding whether the study participant should restart IMP and contact the Medical Monitor and UCB study physician to confirm the participant's suitability for continued participation in the study.

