^c Home visits can be conducted during the OLE Period upon agreement of the Investigator, study participant, and his/her caregiver. For IMP administration at home, see footnote j.

^d Physical examination findings that are clinically significant will be recorded as AEs.

^e Pulse, systolic/diastolic blood pressure, and temperature are to be measured prior to IMP administration and any blood collection.

^f Analyses will be performed by a central laboratory, except urine dipsticks, which will be assessed locally at the site. Participants do not have to be fasting.

Table 1-2: Schedule of study assessments – Open-label Extension Period

Protocol activity	Week ^a	OLE Period																										

^g Pregnancy testing for postmenarchal female participants via urine testing locally (or at home). Pregnancy test results conducted at home will be assessed by caregiver or participant (if > 18 years) or, if present, by the visiting health care professional and must be negative prior to IMP administration. In the case of a positive pregnancy test, the study participant/caregiver must contact the site immediately.

^h IGRA testing is required to be performed by the central laboratory.

ⁱ Post-Baseline scalp IGA will only be completed for participants with a scalp IGA score >0 at Baseline.

^j Dose A and Dose B may be administered at the study site or where possible at home. Dose A of the IMP may be administered by a health care professional, caregiver, or study participant. Administration of Dose A by the caregiver or study participant is optional and requires training, as described in Section 6.2. Dose B must be administered by a health care professional to ensure accurate dosing of the lower volume of IMP. If IMP is administered at home, the administration will be documented as described in Section 6.2.1.

^k Investigational medicinal product will only be administered at Week 20 if the participant continues into the OLE Period.

^l Plasma for BKZ concentration and anti-BKZ antibodies collection should be performed prior to IMP administration.

^m CSSRS to be performed via phone contact if IMP is administered at home.

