8.2.4 Neuropsychiatric AE monitoring/suicidal risk monitoring

At Screening, participants who meet specified thresholds on the C-SSRS or PHQ-9 assessments, as noted in exclusion criteria 30 and 31, will be evaluated by a mental health professional (ie, licensed psychiatrist or clinical psychologist) to determine whether they are eligible for participation. In addition, participants may be referred to a mental health professional during the conduct of the study as outlined in Section 8.2.4.1 and Section 8.2.4.2.

The Medical Monitor will review AEs every 2 weeks for any potential neuropsychiatric AEs (including SIB) and will discuss such AEs with the Investigator. Additionally, neuropsychiatric AEs will be reviewed at periodic DMC meetings.

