8.2.4.2 PHQ-9

The PHQ-9 is a multipurpose instrument for screening, diagnosing, monitoring, and measuring the severity of depression (Kroenke et al, 2001). A validation study has been conducted in adolescents to assess the psychometric properties of the PHQ-9 (Richardson, 2010). The PHQ-9

scores for depression range from 0 to 27, with higher scores indicating worse state. A score of 5 to 9 is considered to be minimal symptoms of depression. A score of 10 to 14 is considered to be minor depression, dysthymia, or mild major depression. A score of 15 to 19 is considered to indicate moderately severe major depression, and a score ≥ 20 is considered to be severe major depression.

The PHQ-9 will be self-administered by the study participant and will be assessed by the study personnel at the visits specified in the Schedule of Activities (Section 1.3).

Refer to Section 7.2 for PHQ-9-related withdrawal criteria.

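### The on-study PHQ-9 referral rule for scores of 15 to 19 misses small-step entries (13 to 15, 14 to 15, 14 to 16), after which a score can climb to 19 with no mandatory PHQ-9 referral

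*Protocol*

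**What the plan says.** Protocol Section 7.2 holds all the PHQ-9 thresholds that act on participants after enrolment.

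- **Item 1** requires withdrawal and immediate referral. Its PHQ-9 limb is "Severe depression as indicated by a PHQ-9 score" of 20 or more.
- **Item 11** requires immediate referral and leaves withdrawal to the Investigator. Its PHQ-9 limb is a "PHQ-9 score of 15 to 19 if this represents an increase of 3 points compared to last visit". It stands under the lead-in "Investigators should contact the Medical Monitor to discuss whether a participant is to be withdrawn from the study".
- Each item also has a C-SSRS limb, worded "Active suicidal ideation as indicated by a positive response": Question 5 in item 1 and Question 4 in item 11. Item 1 adds any suicidal behavior.

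Section 8.2.4 says that "participants may be referred to a mental health professional during the conduct of the study as outlined in Section 8.2.4.1 and Section 8.2.4.2". Section 8.2.4.2 sets no further threshold: "Refer to Section 7.2 for PHQ-9-related withdrawal criteria". It does define the band: "A score of 15 to 19 is considered to indicate moderately severe major depression".

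At entry, exclusion criterion 31 (Section 5.2) keeps out anyone scoring 15 or more and sends screening scores of 10 to 14 to a mental healthcare practitioner. SAP Section 5.6.3.4 tabulates and lists PHQ-9 and contains no referral rule.

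**The concern.** A rule based on change makes sense where participants may enroll with chronically high scores and repeated referrals would serve no purpose. That is not the case here. Scores of 15 or more are excluded at entry, so a first on-study score in the 15-19 band is always a new move into a range the protocol treats as serious depression. Requiring a 3-point jump as well means that a participant who worsens in small steps escapes the rule, while one who worsens by less in total, but in one step, is caught.

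The result is also out of line with the entry rule. A screening score of 10 requires evaluation, but an on-study score of 19 reached in 2-point steps does not.

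Two features of the wording add to the problem. The text does not say that the increase is a minimum. It also compares with the last visit, although in the Open-label Extension (OLE) most visits have no PHQ-9.

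What is at stake is the protection of adolescents whose depression worsens without suicidal ideation at C-SSRS Question 4 or 5 level. The PK endpoint, the efficacy analyses and the sample size are not affected.

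**Working it through.** The plan gives no figure to reproduce, so the check lists every possible score move.

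**Inputs**
- Possible scores before entering the band: 0 to 14, which is 15 values (criterion 31).
- Band: 15 to 19, which is 5 values (Section 7.2 item 11).
- Trigger: new score in the band and a rise of at least 3 from the last PHQ-9. This reading favors the protocol.
- Next PHQ-9 trigger: 20 or more (Section 7.2 item 1).

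**Step 1: entries into the band.** 15 × 5 = 75 pairs. The rise is below 3 in only three of them:

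| Previous | New | Rise | Referral forced by PHQ-9? |
|---|---|---|---|
| 13 | 15 | 2 | No |
| 14 | 15 | 1 | No |
| 14 | 16 | 2 | No |

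The other 75 − 3 = 72 pairs (72/75 = 96%) trigger.

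**Step 2: moves within the band.** There are 5 × 5 = 25 pairs, counting no change. Only 15 to 18, 15 to 19 and 16 to 19 rise by 3 or more. The other 22 do not trigger.

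**Step 3: rising to 19 without a trigger.** Count the strictly rising paths made of steps of 1 or 2.
- From 15 (4 points to climb): 1+1+1+1, 2+1+1, 1+2+1, 1+1+2, 2+2, giving 5 paths.
- From 16 (3 points to climb): 1+1+1, 2+1, 1+2, giving 3 paths.
- The three missed entries land on 15, 15 and 16, so there are 5 + 5 + 3 = 13 untriggered paths.
- The total rise is 19 − 13 = 6 or 19 − 14 = 5 points.
- The shortest paths take three assessments counting the entry step, for example 13, 15, 17, 19. The longest take five.

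**Step 4: how long the shortest climb takes.** From entry to 19 needs at least two further assessments. In Table 1-1, PHQ-9 is marked at every 4-weekly visit from Baseline, so that is 2 × 4 = 8 weeks in the Initial Treatment Period.

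The week headings of Table 1-2 did not survive text extraction, so its spacing is inferred. The table marks plasma sampling in columns 1, 6, 12, 18 and 24, and SAP Section 5.7.1.1 gives OLE sampling at Weeks 20, 40, 64, 88 and 112. That fits week = 20 + 4 × (column − 1); for example, column 12 gives 20 + 44 = 64. PHQ-9 is marked in columns 1, 3, 6, 9, 12, 15, 18, 21 and 24, and once more in column 28. This puts it 12 weeks apart after Week 28, so two further assessments take about 2 × 12 = 24 weeks.

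**Step 5: the comparator in the OLE.** PHQ-9 is marked in 10 of 29 columns of Table 1-2, and C-SSRS in all 29. For every marked PHQ-9 column after the first, the column just before it has no PHQ-9. The comparison can only work if last visit means the last PHQ-9 assessment, which the protocol does not say.

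**Step 6: the literal reading.** If the increase must be exactly 3, only 12 to 15, 13 to 16 and 14 to 17 trigger, and 72 of 75 entries are missed. I do not rely on this reading, but the wording permits it.

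**The case against.** The best defense is that item 11 deliberately pairs an absolute band with a change criterion, in monitoring that Amendment 1 added in response to FDA recommendations. Any change threshold lets small moves through, and this one catches 96% of entry pairs. Nothing in the documents shows that a 1- or 2-point move across 15 needs specialist referral.

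There are also other safeguards. C-SSRS Question 4 or 5, or any suicidal behavior, forces referral whatever the PHQ-9 score, and home dosing does not interrupt this: "CSSRS to be performed via phone contact if IMP is administered at home". Study personnel see each PHQ-9 score. The Medical Monitor reviews AEs every 2 weeks for neuropsychiatric events, and the DMC reviews them periodically. The Investigator can refer, stop dosing or withdraw a participant at any time.

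These points hold and keep the finding small, but they do not close the gap. The C-SSRS triggers detect suicidality, not depression without it. AE review depends on an AE being reported, and a PHQ-9 score is not automatically one. Investigator judgment is what a mandatory referral rule is meant to back up.

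Three limits stand. Pair and path counts are not risks, and in a study of about 40 participants the number affected could be zero. The proposed change acts only on the first score of 15 or more, so later small-step worsening, or a fall below 15 and a slow return, would still not trigger; anyone in that position would already have been referred once. Finally, SAP version 3.0 (09 Apr 2025) gives database lock among its reasons, so there may be little time left to amend.

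**Conclusion.** The concern holds, as a minor point of participant safety. On the reading most favorable to the protocol, three of 75 entries into the 15-19 band carry no mandatory PHQ-9 referral and no Medical Monitor contact under item 11. From those entries a score can remain in the band or reach 19 untriggered.

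The conclusion rests on three things: Section 7.2 contains the only on-study PHQ-9 triggers, enrolled participants start at 14 or below, and the increase is read as at least 3 points from the last PHQ-9. The counts are exact under those conditions. The 24-week OLE timing is an inference, and the finding does not depend on it. How many participants would be affected cannot be estimated from the documents.

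**What to change.** In Protocol Section 7.2 item 11, replace the condition attached to the 15-19 band with:

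> if this is an increase of at least 3 points from the previous PHQ-9 assessment, or is the first on-study score of 15 or more

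This closes all three missed entries (75 of 75 then trigger), makes the 3 points a minimum and fixes the comparator in the OLE. For participants below 15 at their previous assessment, the added condition creates new referrals only for the three missed pairs, because every other first score of 15 or more already triggers. It adds at most one mandatory referral per participant and uses an existing pathway.

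The cost is one sentence in a protocol amendment. That needs IRB/IEC approval (Section 10.1.1), so it is best bundled with the next amendment. No SAP change is needed. If conduct is too far advanced to amend, the PHQ-9 listing already planned in SAP Section 5.6.3.4, which shows change from the previous visit, lets the sponsor check whether anyone passed through the gap.

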7.3 Lost to follow up

A participant will be considered lost to follow up if he or she repeatedly fails to return for scheduled visits and is unable to be contacted by the study site.

The following actions must be taken if a participant fails to return to the clinic for a required study visit:

- The site must attempt to contact the participant and reschedule the missed visit as soon as possible and counsel the participant on the importance of maintaining the assigned visit schedule and ascertain whether or not the participant wishes to and/or should continue in the study.
- Before a participant is deemed lost to follow up, the Investigator or designee must make every effort to regain contact with the participant (at least 1 phone call and 1 written message

to the participant), and document his/her effort (date and summary of the phone call and copy of the written message in the source documents), to complete the final evaluation (EDV and SFU, as applicable). All results of these evaluations and observations, together with a narrative description of the reason(s) for removing the participant, must be recorded in the source documents. The eCRF must document the primary reason for withdrawal.

Should the participant continue to be unreachable, he/she will be considered to have withdrawn from the study with a primary reason of lost to follow up documented in the eCRF.

8 STUDY ASSESSMENTS AND PROCEDURES

Study procedures and their timing are summarized in the Schedule of Activities ([Table 1-1](#) and [Table 1-2](#)). An unscheduled visit(s) can be conducted if necessary.

Protocol waivers or exemptions are not allowed.

Immediate safety concerns should be discussed with the Sponsor immediately upon occurrence or awareness to determine if the participant should continue or discontinue IMP.

Adherence to the study design requirements, including those specified in the Schedule of Activities, is essential and required for study conduct.

All screening evaluations must be completed and reviewed to confirm that potential participants meet all eligibility criteria. The Investigator will maintain a screening log to record details of all participants screened and to confirm eligibility or record reasons for screening failure, as applicable.

Procedures conducted as part of the participant's routine clinical management (eg, blood count) and obtained before signing of the ICF may be utilized for screening or Baseline purposes provided the procedures met the protocol-specified criteria and were performed within the time frame defined in the Schedule of Activities.

The maximum amount of blood collected from each participant over the duration of the study, including any extra assessments that may be required, will not exceed the maximum volume of blood as specified by IRB/IEC requirements. Repeat or unscheduled samples may be taken for safety reasons or for technical issues with the samples.

8.1 Efficacy assessments

All efficacy assessments are considered appropriate for, and applicable to, adolescents.

8.1.1 Psoriasis Area and Severity Index

The PASI is the most commonly used and validated assessment for grading the severity of PSO in clinical studies (Feldman, 2004). The PASI quantifies the severity and extent of the disease and weighs these with the percentage of BSA involvement. The PASI will be completed as specified in [Table 1-1](#) and [Table 1-2](#). The PASI will be completed by the Investigator.

The percent area of involvement (BSA%) is estimated across 4 body areas; head, upper extremities, trunk, and lower extremities. Assessors will enter the degree of involvement for a given region on a scale of 0 to 6 (0=none; 1=1% to <10% affected, 2=10% to <30% affected, 3=30% to <50% affected, 4=50% to <70% affected, 5=70% to <90% affected, 6=90% to 100% affected) ([Table 8-1](#)).

The Investigator assesses the average redness, thickness, and scaliness of lesions in each body area (each on a 5-point scale); 0=none, 1=slight, 2=moderate, 3=marked, and 4=very marked.

The PASI score ranges from 0 to 72 with a higher score indicating increased disease severity.

Table 8-1: Body areas for calculation of percent BSA for PASI

Body area	Details of area	BSA	Degree of involvement of body area ^a
Head	Face, back of head	10%	0 to 6
Upper extremities	Left, right, upper lower, flexor surface, extensor surface	20%	0 to 6
Trunk	Front, back, groin	30%	0 to 6
Lower extremities	Left, right, upper lower, flexor surface, extensor surface, including buttocks	40%	0 to 6
Total		100%	

BSA=body surface area; PASI=Psoriasis Area and Severity Index

^a Where 0=none; 1=1% to <10% affected; 2=10% to <30% affected; 3=30% to <50% affected; 4=50% to <70% affected; 5=70% to <90% affected; 6=90% to 100% affected.

The PASI50, PASI75, PASI90, and PASI100 responses are based on at least 50%, 75%, 90%, and 100% improvement in the PASI score, respectively.

The total BSA affected by PSO will be entered as a percentage from 0 to 100.

8.1.2 Investigator's Global Assessment

A static IGA for PSO will be used to assess disease severity in all participants during the study. The IGA will be completed as specified in Table 1-1 and Table 1-2. The IGA will be completed by the Investigator.

The Investigator will assess the overall severity of PSO using the following 5-point scale presented in Table 8-2.

Table 8-2: Five-point IGA

Score	Short descriptor	Detailed descriptor
0	Clear	No signs of PSO; post-inflammatory hyperpigmentation may be present
1	Almost clear	No thickening; normal to pink coloration; no to minimal focal scaling
2	Mild	Just detectable to mild thickening; pink to light red coloration; predominately fine scaling
3	Moderate	Clearly distinguishable to moderate thickening; dull to bright red; moderate scaling

4	Severe	Severe thickening with hard edges; bright to deep dark red coloration; severe/coarse scaling covering almost all or all lesions
---	--------	---

IGA=Investigator's Global Assessment; PSO=psoriasis

